9.6.4 Analyses of Secondary Endpoints

All secondary analyses will primarily be summarised descriptively based on the FAS, unless otherwise specified.

The change in secondary endpoints such as serum bile acids, growth, APRI score, Fib-4 score, PELD/MELD will be summarised by visit using descriptive statistics.

❖ Growth

Change in growth (height/length for age, weight for age, mid-arm circumference for age, and BMI for age) will be analysed by using the 1-sample t-test or the Wilcoxon signed

rank test, as appropriate at the end of the 72-week treatment period based on the average of the values at Weeks 70 and 72. In addition, change in growth will also be displayed using graphical presentations. Baseline 1 and 2, defined in the table of derived variables in [Appendix A](#), will be used to calculate change from baseline for data analysis. Baseline 1 will only be used for patients in Cohort 1 who were on odevixibat in Study A4250-005.

The analysis of growth data for height/length, weight, and BMI will be based on calculated values using the software or methods from the Centers for Disease Control and Prevention (CDC) website for patients with age ≥ 2 years old and from the WHO website for patients with age < 2 years old^{7,8}. The analysis of growth data for mid-arm circumference will be based on calculated values for 2 months to 18 years for U.S. Children⁹. CRF collected growth data will be listed.

❖ Serum Bile Acids

For serum bile acids assessments, if a patient has assessments at Weeks 70 and 72, then the average of the 2 assessment values at Weeks 70 and 72 will be used for data analysis. This handling will also be applied to Weeks 22 and 24, and Weeks 46 and 48.

❖ Proportion of Positive Pruritus

The proportion of individual assessments meeting the definition of a positive pruritus assessment at the patient level on the Albireo ObsRO instrument from Weeks 0-4, Weeks 0-12, Weeks 0-22, Weeks 0-24, Weeks 0-36, Weeks 0-46, Weeks 0-48, Weeks 0-60, Weeks 0-70, or the proportion of positive pruritus assessments at each 4-week interval between Visit 1/Screening and Visit 5/Week 24, then by each visit between Visit 5/Week 24 to Visit 12/Week 76 will be summarised descriptively as for the primary analysis for the US. Similar summaries will be provided based on AM scores as well as PM scores.

⁷ <https://www.cdc.gov/nccdphp/dnpao/growthcharts/resources/sas.htm> following CDC's method

⁸ <https://www.cdc.gov/nccdphp/dnpao/growthcharts/resources/sas-who.htm> following WHO's method

⁹ Abdel-Rahman, Susan M et al. "Construction of Lambda, Mu, Sigma Values for Determining Mid-Upper Arm Circumference z Scores in U.S. Children Aged 2 Months Through 18 Years." *Nutrition in clinical practice* : official publication of the American Society for Parenteral and Enteral Nutrition vol. 32,1 (2017): 68-76.

The number and percent of patients achieving positive pruritus assessment for more than 50% of the time will be summarised by treatment group. Both AM and PM pruritus assessments will be included in the analysis of this endpoint. A cumulative distribution function (CDF) plot showing proportions of patients achieving positive pruritus assessment for more than X% of the time, X is the time of achieving positive pruritus assessment from 0 to 100%, by treatment group will be provided.

❖ Proportion of Responders for Pruritus Scores

The proportion of responders for pruritus scores will be tabulated by visit based on monthly scores and bi-weekly scores. The 95% CI of the proportion of responders will be provided, based on the exact method of Clopper-Pearson. A responder is defined as a patient who reports a decrease in pruritus score from unrounded baseline equivalent to or greater than the threshold of meaningful change estimated from the blinded psychometric analysis; the results of the blinded psychometric analysis across all anchors support a threshold of 1.0 point for AM, PM and AM and PM scratching scores. Baseline 1 and 2, defined in the table of derived variables in [Appendix A](#), will be used for data analysis. Baseline 1 will only be used for patients in Cohort 1 who were on odevixibat in Study A4250-005.

❖ Biliary Diversion Surgery and Liver Transplantation

Number and percent of patients undergoing biliary diversion surgery and/or liver transplantation will be summarised by using descriptive statistics. A 95% CI also will be presented for the corresponding percentage. These parameters will be evaluated separately and together at Weeks 24, 48, 72 and all visits (every 16 weeks) during the optional extension period.

Kaplan-Meier curves will be used when appropriate for time-to-event data (that is, time to biliary diversion surgery or liver transplantation or death and time to any event). If a patient does not have any event, the patient will be censored at the last contact date. Median event-free times and associated 95% CIs will be calculated using Brookmeyer and Crowley methodology and a log-log transformation for constructing CIs.

❖ Fibroscan®

The change in APRI and Fib-4 score will be summarised using descriptive statistics from baseline 2 to Week 72 and all visits (every 16 weeks) during the optional extension period.

❖ PELD and MELD Score

The change in PELD and MELD will be summarised separately using descriptive statistics from baseline 2 to Week 72 and all visits (every 16 weeks) during the optional extension period.

❖ UDCA and/or Rifampicin

Percentages of patients in use of UDCA and/or Rifampicin at weeks 24, 48, and 72 will be presented in 4 categories, use of UDCA, use of Rifampicin, use of UDCA or Rifampicin, use of UDCA and Rifampicin. Percentage will be based on patients in study at week 24, 48, and 72.

Shift tables from Baseline 2 in use of UDCA and/or Rifampicin at Weeks 24, 48, and 72 will be presented in the following categories. “None”, “UDCA alone”, “Rifampicin alone”, “UDCA and Rifampicin”, “Early Termination”. Percentage will be based on patients in study at week 24, 48, and 72.

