3.1 General Study Design

This is a Phase 3, multicentre, open-label extension study to investigate the long-term efficacy and safety of odevixibat at doses of 40 and 120 µg/kg/day in patients with PFIC, including episodic forms also referred to as benign recurrent intrahepatic cholestasis (BRIC). Cohort 1 includes children with PFIC Types 1 and 2 who have participated in Study A4250-005. Cohort 2 includes patients with any type of PFIC who have elevated serum bile acids and cholestatic pruritus and who either (1) did not meet eligibility criteria for Study A4250-005 (PEDFIC 1) or (2) were eligible for enrolment in Study A4250-005 after recruitment of Study A4250-005 completed. Up to 40 patients' post-biliary diversion surgery were allowed to participate in Cohort 2.

Study data are reviewed periodically (approximately on a quarterly basis) by a Data Safety and Monitoring Board (DSMB) until the last patient reaches 72 weeks.

Informed consent must have been obtained before any study procedures were performed. After signing the informed consent form (ICF), patients were evaluated for study eligibility and considered to be enrolled in the study. For Cohort 1, patients were eligible to participate in this extension study if they completed the 24 weeks of treatment in Study A4250-005, or, prior to amendment 6 of the A4250-005 protocol, withdrew from Study A4250-005 after a minimum of 12 weeks of treatment with odevixibat due to

patient/caregiver judgment of no improvement/intolerable symptoms but met all inclusion criteria and no exclusion criteria. Patients who withdrew from Study A4250-005 due to a study drug-related adverse event (AE) were not eligible. For Cohort 2, patients meeting all inclusion criteria and no exclusion criteria were eligible.

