4.4 Safety Evaluation

Safety criteria are as follows:

- The primary safety analysis for this study will include the incidence of total treatment-emergent adverse events (TEAEs) and TEAEs categorised by causality, severity, and seriousness assessments made by the Investigator.
- Trends in safety will also be evaluated for the following:
 - Physical examinations
 - Concomitant medications
 - Vital signs
 - Laboratory test results (including clinical chemistry, haematology, urinalysis, alfa-fetoprotein [AFP], vitamins A and E, 25-hydroxy vitamin D, and INR)
 - Abdominal ultrasound
 - Discontinuations due to AEs

5. Sample Size and Power

There is no formal hypothesis testing in this open-label study. The sample size for Cohort 1 was determined in Study A4250-005. For Cohort 1, patients will be enrolled after completion of Study A4250-005 or participation of 12 weeks in that study. For the other endpoints, mainly descriptive analyses will be performed.

The proportion of patients with at least 1 event (i.e., surgical bile diversion, liver transplantation, death) that can be expected in a non-treated population depends on PFIC type and age distribution of the included patients. The expected proportion of patients with events will be calculated for the study population once each patient's age and PFIC type are known, using the probability that a patient will get an event estimated from the reference population in the ongoing observational cohort study, NAtural Course and Prognosis of PFIC and Effect of Biliary Diversion (NAPPED).

As an example, if the expected proportion of patients with at least 1 event is estimated to be 30% in the study population, and then if the proportion of patients with at least 1 event during odevixibat long-term treatment is shown to be only 10% in the study, the power is approximately 89% to 96% (1-sided test, alpha=2.5%) for a confidence interval (CI) with upper boundary <30% based on a sample size of n=48 to 60. The sample size of 60 for Cohort 2 was estimated based on the availability of target patient population to evaluate the therapeutic benefit for those patients.

6. Interim Analysis

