This study is an extension study of Study A4250-005 and was ongoing at the time of the New Drug Application (NDA) and Marketing Authorisation Application (MAA) submission in November 2020. For the NDA/MAA submission purposes, the database was locked on 31Aug2020 for Study A4250-005, and an interim analysis of Study A4250-008 with data cut on 15Jul 2020 was performed to accompany the final analyses of Study A4250-005.

For this interim analysis submitted in the NDA/MAA, the analyses described in this SAP were conducted, as appropriate, based on data available at the time of the data cut-off date. The interim analysis was conducted for both safety and efficacy mainly based on descriptive statistics. The main time point was at the end of 24-week treatment period

while all data were included for by-visit summaries. These analyses accompanied the Study A4250-005 analyses and provided further information regarding the safety and efficacy of odevixibat dosing for more than 24 weeks.

For supporting a post-marketing commitment, an interim analysis of Study A4250-008 (planned data cut of 31July2022) was performed in order to update the CSR. The selected analyses described in this SAP were conducted, as appropriate, for the interim analysis based on data available at the time of the data cut-off date. The interim analysis was conducted for both safety and efficacy mainly based on descriptive statistics.

Analyses may be performed at select time points throughout the collection of patient data for regulatory requirements and sponsor decision making purposes.

7. Analysis Sets

The FAS will consist of all patients who received at least 1 dose of study drug in Study A4250-008. The FAS will be the primary analysis set for all analyses unless otherwise specified.

8. Statistical Considerations and Analysis

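### Biliary diversion is reported on all dosed patients, although up to 40 Cohort 2 patients may already have had one; the Cohort 2 and Overall diversion rates are diluted and no rule covers prior or repeat diversion

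*SAP*

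**What the plan says.** - **Entry.** Section 3.1: "Up to 40 patients' post-biliary diversion surgery were allowed to participate in Cohort 2". Section 5 adds: "The sample size of 60 for Cohort 2 was estimated based on the availability of target patient population".
- **Analysis set.** Section 7: "The FAS will consist of all patients who received at least 1 dose of study drug in Study A4250-008". Section 9.6.4 opens with: "All secondary analyses will primarily be summarised descriptively based on the FAS, unless otherwise specified".
- **Endpoint.** Section 9.6.4: "Number and percent of patients undergoing biliary diversion surgery and/or liver transplantation will be summarised by using descriptive statistics". A 95% CI accompanies the percentage. Diversion and transplantation are evaluated separately and together at Weeks 24, 48 and 72 and at each extension visit.
- **Time to event.** Section 9.6.4 plans Kaplan-Meier curves, when appropriate, for "time to biliary diversion surgery or liver transplantation or death and time to any event", with event-free patients censored at last contact. Section 9.7.1 allows a further curve for time to biliary diversion surgery.
- **Expected rate.** Section 5: "The expected proportion of patients with events will be calculated for the study population once" age and PFIC type are known for each patient. Prior diversion is not named as a factor.
- **Columns.** Section 9.1 plans four: two Cohort 1 groups, Cohort 2, and Overall.
- **Silent on this point.** Prior diversion is not among the disease characteristics of Section 9.4.2 or the subgroups of Section 9.8.1, and those subgroups apply only to the primary endpoints. Section 9.2 counts patients who have undergone diversion without saying whether before or during the study.

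**The concern.** Section 2.2 makes the effect of odevixibat on diversion and transplantation a secondary objective. A patient whose diversion preceded the first dose cannot have a first diversion on study. Under the plan that patient still sits in the denominator, counts as free of diversion, and is carried in the risk set until last contact. The percentage falls, its confidence limits move down with it, and the event-free curve rises, all because of who was enrolled and not because of what the drug did. The distortion runs in one direction for any number of such patients above zero. The SAP also leaves open whether a revised or second diversion is an event, so two programmers could produce different counts from the same data.

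**Working it through.** **Inputs.** Planned Cohort 2 size N = 60 (Section 5). Number with prior diversion k, at most 40 (Section 3.1); the enrolled number is not in the SAP. Denominator: all dosed patients (Sections 7 and 9.6.4). Assumption: prior-diversion patients have no further diversion on study. CIs below are exact (Clopper-Pearson); Section 9.6.4 names that method for pruritus responders but none for this endpoint.

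**The plan's own figure.** Section 5 states power of about 89% to 96% that the upper confidence bound lies below 30% when the true event proportion is 10%, one-sided alpha 2.5%, n = 48 to 60. With the exact bound:
- n = 48: the bound is below 30% for 7 or fewer events; P(X ≤ 7 | 48, 0.10) = 89.8%.
- n = 60: the bound is below 30% for 10 or fewer events; P(X ≤ 10 | 60, 0.10) = 96.6%.

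The stated power is reproduced. It treats all n patients as exposed to the same event risk.

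**Diversion alone, Cohort 2.** Reported rate = at-risk rate × (60 − k)/60.

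| k | At risk | Factor | A 30% at-risk rate is shown as |
|---|---|---|---|
| 0 | 60 | 1.00 | 30% |
| 5 | 55 | 0.92 | 27.5% |
| 10 | 50 | 0.83 | 25% |
| 20 | 40 | 0.67 | 20% |
| 30 | 30 | 0.50 | 15% |
| 40 | 20 | 0.33 | 10% |

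At the cap, 6 diversions among 20 at-risk patients are 6/20 = 30% (CI 11.9% to 54.3%). On the FAS they are shown as 6/60 = 10% (CI 3.8% to 20.5%).

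**Diversion alone, Overall.** The Cohort 1 size is not fixed in the SAP. If it were 48 to 60 (an assumption), Overall would hold 108 to 120 patients. The factor at k = 40 would then be 68/108 = 0.63 to 80/120 = 0.67, and at k = 10 it would be 98/108 = 0.91 to 110/120 = 0.92.

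**Cohort 1 columns.** Section 3.1 mentions post-diversion patients only for Cohort 2, so no dilution is shown there.

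**Composite.** Prior-diversion patients can still be transplanted or die, so only the diversion part is diluted. As an illustration at the cap, take 6 events among the 20 at-risk patients and assume 10% transplantation or death among the other 40, which is 4 events. The FAS composite is (6 + 4)/60 = 16.7% (upper limit 28.5%), compared with 10% if those 40 had no events at all.

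**The case against.** The strongest reply is that the SAP tests nothing here. Section 5 states that there is no formal hypothesis testing, Section 9.6.4 is descriptive, and Section 10 moves the natural-history comparison to a separate analysis whose handling of prior diversion cannot be seen. That stands. What this SAP produces directly is a diluted rate, interval and curve, not a false test result.

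A reader might go further and infer that an inactive drug would reproduce the 30% versus 10% contrast of Section 5, since 30% among at-risk patients appears as 10% at the cap. The documents do not support that. Forty is a ceiling and the enrolled number is not given. The Section 5 example concerns a composite with transplantation and death, to which prior-diversion patients remain exposed. Section 5 also does not tie the example to Cohort 2, and no decision rule in this SAP acts on it.

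Two further objections stand in part. The endpoint speaks of patients undergoing diversion, not a first diversion, so zero further risk is an assumption; this makes a stated rule for repeat diversion more necessary. Surgical history is summarised and listed (Section 9.4.3), so affected patients can be identified, but a listing does not correct a percentage or a curve.

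**Conclusion.** The point holds for the diversion-alone rate in the Cohort 2 and Overall columns, and for the diversion component of the composite there. If prior-diversion patients have no further diversion, the Cohort 2 rate is multiplied by a factor between 1 (k = 0) and 0.33 (k = 40). The loss is already 17% of the rate at k = 10 and 33% at k = 20. Where the factor lies depends on the enrolled k, which the SAP does not state.

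The direct consequence is a misleading descriptive result on a stated objective. It becomes a bias in favour of the drug only if the observed rate is read against an untreated expectation that ignores prior diversion, which is how Section 5 defines that expectation. Whether the separate natural-history comparison shares the fault cannot be judged from this SAP.

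**What to change.** - **Section 9.6.4, diversion alone.** Use patients with no diversion before the first odevixibat dose as denominator and Kaplan-Meier risk set, and apply the same to any Section 9.7.1 curve for diversion.
- **Section 9.6.4, composite** (diversion, transplantation or death). Present it in the full FAS and by prior-diversion status (yes/no). Do not drop prior-diversion patients from it, because their transplantations and deaths are genuine events.
- **Repeat diversion.** State whether a repeat or revised diversion counts as an event, and in which analysis.
- **Section 5.** Account for prior diversion when computing the expected proportion, so that no patient is assigned the risk of a first diversion that has already happened.

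The cost is SAP wording and one baseline flag from surgical history that is already collected and coded. The at-risk number is smaller and the CI wider: at the cap, 20 patients in place of 60, as in the 6/20 example above.

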- Visit 11: Week 72/optional extension period
- Visit 12: Follow-up visit; Week 76 (for those not participating in optional extension period)
- Optional extension period visits every 16 weeks; Week 88 and onwards

Figure 1 Study Design

[figure not shown]

QD: once daily; T: telephone contact; V: study visit; VS: Visit Screening

Note: Visit 1 coincides with Visit 9 of Study A4250-005. Patients who are not tolerating the 120 µg/kg/day dose may be down-titrated to the 40 µg/kg/day dose following a minimum of 1 week of treatment. The patient can return to the higher dose as soon as deemed appropriate.

This figure is only applicable to Cohort 2 up to Protocol Amendment 5. [Figure 2](#) presents the study design for Cohort 2 as of Protocol Amendment 6.

Figure 2 Study Design for Cohort 2 as of Protocol Amendment 6

QD: once daily; T: telephone contact; V: study visit; VS: Visit Screening

Note: As of Protocol Amendment 6, patients entering Cohort 2 will start treatment at 40 µg/kg/day with the possibility to dose escalate to 120 µg/kg/day after 12 weeks if there is no improvement in pruritus based on investigator judgment. The patient can return to the lower dose if the 120 µg/kg/day dose is not tolerated following a minimum of 1 week of treatment.

Patients were to return to the clinic at Weeks 4 and 12 and thereafter every 10 to 12 weeks for follow-up measurements. Between clinic visits there was to be a telephone contact with the patient and/or caregiver to report AEs. Additional clinic visits may have been required for patients who needed direct site assistance for AE monitoring for safety maintenance and other assessments.

At Visit 11, patients were to be offered the choice to continue receiving odevixibat treatment in an optional extension period. During the optional extension period the patient was to receive odevixibat at the same dose as at the end of the 72-week treatment

period, returning to the clinic every 16 weeks until the drug is commercially available, provided continued use was supported by the risk-benefit profile and the patient had not been previously withdrawn or discontinued from study.

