If a patient was prematurely withdrawn from the study prior to Week 72, all assessments scheduled for Visit 11 were to be performed at the time the patient withdrew. If a patient participating in the optional extension study withdrew prior to commercial drug availability, all assessments scheduled for the optional extension period EOT visit were to be performed.

If a liver biopsy was performed according to the local regulations or standard of care at any time during A4250-008, the biopsy results should have been recorded in the electronic case report form (eCRF). If liver biopsy results were collected for a patient in Study A4250-005 or prior to Week 24 in Study A4250-008, the patient was to be asked to consent to a follow-up liver biopsy at Visit 11, if allowed per local regulations, unless 2 prior liver biopsy results had been collected (with at least 1 year between biopsies). Liver biopsies were not performed in Spain.

For patients not participating in the optional extension period, Visit 12 was to take place 28 days after Visit 11. All patients who were prematurely withdrawn were to have this visit 28 days after the last dose of study drug for AE monitoring and other safety follow-up assessments.

If a patient discontinued before Week 72, additional telephone contacts were to be made every 3 months after the Follow-up visit (Visit 12) up to Week 72 to inquire whether the patient had undergone biliary diversion or liver transplantation, and if ongoing TEAEs at the time of discontinuation had resolved. The telephone calls were to take place up until 72 weeks even if the patient had biliary diversion or liver transplant.

Patients and/or caregivers were instructed to complete the electronic diary (eDiary) every morning and evening for the first 24 weeks (Visits 1 to 5) and for the 21 days before each clinic visit thereafter (Visits 6 to 12). In addition, Cohort 2 patients and/or caregivers were instructed to complete the eDiary during the Screening period. Patients participating in the optional extension period were not to complete eDiary entries after Visit 11. The eDiary included patient-reported outcome (PRO) and observer reported outcome (ObsRO) items for evaluation of itching (using PRO), scratching (using ObsRO), and

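### Diversion and transplant percentages at extension visits: on the default FAS reading, rates from Week 88 on are understated because planned event follow-up ends at Week 72 or 76 for patients outside the extension

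*SAP*

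**What the plan says.** **What is reported.** In its paragraph on the two procedures, SAP Section 9.6.4 says: "Number and percent of patients undergoing biliary diversion surgery and/or liver transplantation will be summarised by using descriptive statistics". Each percentage carries a 95% CI. On timing: "These parameters will be evaluated separately and together at Weeks 24, 48, 72 and all visits (every 16 weeks) during the optional extension period". Section 3.1 starts the extension visits at Week 88.

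**Denominator.** The opening of Section 9.6.4 sets the default: "All secondary analyses will primarily be summarised descriptively based on the FAS, unless otherwise specified". Section 7 defines that set: "The FAS will consist of all patients who received at least 1 dose of study drug in Study A4250-008". The diversion and transplant paragraph specifies no other denominator and does not say whether the count at each visit is cumulative. The paragraph on UDCA and rifampicin in the same section does limit its percentages to patients still in the study at the time point.

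**Event follow-up.** Section 3.1 says that for patients who stop before Week 72, "additional telephone contacts were to be made every 3 months after the Follow-up visit (Visit 12) up to Week 72", asking about diversion and transplantation. It adds: "The telephone calls were to take place up until 72 weeks even if the patient had biliary diversion or liver transplant". The extension is optional: "At Visit 11, patients were to be offered the choice to continue receiving odevixibat treatment in an optional extension period". Completers who decline it have their last visit at Week 76.

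**Time-to-event analysis.** Section 9.6.4 allows Kaplan-Meier curves where appropriate, for the composite of diversion, transplantation or death and for any event, censoring event-free patients at last contact. The only summary it specifies is the median event-free time with its CI. Section 9.7.1 says that Kaplan-Meier curves may be used for, among others, time to biliary diversion surgery.

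**The concern.** The percentage is ordered at visits where part of its default denominator is no longer observed. From Week 88 on, a patient who left at or before Week 72, or declined the extension, stays in the FAS but can add no event. A cumulative FAS percentage therefore treats that patient as event-free without anyone having asked. The error runs one way, downwards, and grows with each visit. The CI treats the full FAS as observed, so it is also narrower than the follow-up supports.

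The effect of treatment on diversion and transplantation is a stated secondary objective (Section 2.2). Late percentages that are too low would make long-term need for surgery look smaller than the data can show.

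**Working it through.** **The plan's own figure.** Section 5 gives a power of about 89% to 96% for an upper confidence bound below 30% when the true event proportion is 10%, with n = 48 to 60 and one-sided alpha 2.5%. With an exact Clopper-Pearson bound, at most 7 events are allowed at n = 48 (power 89.8%) and at most 10 at n = 60 (power 96.6%). The figure reproduces. The present point does not depend on it.

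**Who is observed when.**

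| Patients | Planned event follow-up (Section 3.1) | In FAS denominator at Week 88 and later |
|---|---|---|
| Stop before Week 72 | to Week 72, by telephone | yes |
| Complete, decline extension | to Week 76 | yes |
| Enter extension | every 16 weeks while in the extension | yes |

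Up to Week 72 the whole FAS is followed by design. After Week 76 only the third row is.

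**Inputs for the size (all assumed, because the SAP gives none).**
- 100 FAS patients, 5 with an event by Week 72.
- Constant hazard: -ln(0.95)/72 = 0.00071 per week.
- E = 50 or 30 event-free patients enter the extension, all followed to the week in question.
- Leavers have the same risk as entrants and are observed to Week 72.

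**Formulas.** The probability of an event between Week 72 and week w, given none by Week 72, is q(w) = 1 - 0.95^((w - 72)/72).
- True cumulative risk = 1 - 0.95 × (1 - q). Kaplan-Meier estimates this under non-informative censoring.
- FAS percentage = 5 + E × q.
- Shortfall in percentage points = (95 - E) × q.

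**Week 120.** q = 1 - 0.95^(48/72) = 0.0336.
- True: 1 - 0.95 × 0.9664 = 8.2%.
- E = 50: 5 + 50 × 0.0336 = 6.7%; shortfall 45 × 0.0336 = 1.5 points.
- E = 30: 5 + 30 × 0.0336 = 6.0%; shortfall 65 × 0.0336 = 2.2 points.

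| Week | q | True | FAS, E = 50 | FAS, E = 30 | Shortfall (points) |
|---|---|---|---|---|---|
| 88 | 0.0113 | 6.1% | 5.6% | 5.3% | 0.5 to 0.7 |
| 120 | 0.0336 | 8.2% | 6.7% | 6.0% | 1.5 to 2.2 |
| 168 | 0.0661 | 11.3% | 8.3% | 7.0% | 3.0 to 4.3 |

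If every non-entrant were a completer seen at Week 76, q(76) = 1 - 0.95^(4/72) = 0.0028, and the Week 120 shortfall would be (95 - E) × (0.0336 - 0.0028), or 1.4 to 2.0 points.

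**Sensitivity to the event rate.** Take 10% events by Week 72, with a share L = 10% to 50% of the FAS unobserved afterwards. The FAS percentage is (1 - L) × F(w) + L × F(72), so the shortfall is L × (F(w) - F(72)).
- Week 104 (true 14.1%): 0.4 to 2.1 points.
- Week 120 (true 16.1%): 0.6 to 3.1 points.
- Week 168 (true 21.8%): 1.2 to 5.9 points.

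The direction does not change. The size depends on uptake and event rate.

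**The case against.** **The denominator is not actually fixed.** The FAS names an analysis population; it does not by itself say that by-visit counts are cumulative over all of it. Section 8.1.1 rules out imputation, which weighs against counting unobserved patients as event-free. This stands in part, so a reader may not infer that the SAP commits to a biased estimate. The default still points to the FAS. Section 8.1.1 also exempts this endpoint from the exclusion of late and post-event data, which fits a cumulative count. The alternatives are no better: a denominator of patients seen at the visit loses those who had surgery and left, so the rate could fall over time.

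**Censored analyses are already planned.** True, and not only for the composite with death: Section 9.6.4 adds time to any event and Section 9.7.1 adds biliary diversion. But all are conditional, and no estimate at each visit is specified. If fewer than half the patients have an event, the median is not reached. The FAS percentage is then the only by-visit figure specified. The disposition table (Section 9.2) will show how many patients were not followed, but does not correct the percentages.

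**The analysis is descriptive.** This stands. Section 5 states that there is no formal hypothesis testing, and Section 10 moves the comparison with the natural-history cohort outside this SAP. A reader might infer that the understatement feeds into that comparison; the document does not support this.

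**A larger gap is easy to construct.** With 5% events over 72 weeks and then 10% of entrants over the next 48, Kaplan-Meier gives 1 - 0.95 × 0.90 = 14.5%, against FAS percentages of 10.0% (50 enter) or 8.0% (30 enter). That is a gap of 4.5 to 6.5 points. But the weekly hazard then rises from 0.00071 to -ln(0.90)/48 = 0.00220, about threefold, and nothing in the document supports such a rise.

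**Conclusion.** The point holds conditionally. If the by-visit counts are cumulative over the FAS, which is the default reading but is not stated, the percentages from Week 88 on are understated and the shortfall grows with time. With 5% events by Week 72, a constant hazard, equal risk in leavers and 30% to 50% entering the extension, it is about 1.5 to 2.2 percentage points at Week 120. With high uptake it would be small.

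A reader might infer that the Week 24, 48 and 72 percentages share the problem. They do not, because planned follow-up covers the whole FAS to Week 72. A reader might also infer that leavers are at higher risk, so that the true gap is larger. That is possible, but the document gives no evidence for it, and if true it would bias the Kaplan-Meier estimate downwards as well.

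**What to change.** In Section 9.6.4:

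- Keep the FAS percentage with 95% CI for Weeks 24, 48 and 72, and state that the counts are cumulative.
- For Week 88 and later, replace it with the Kaplan-Meier cumulative estimate, 95% CI and number at risk for diversion or transplantation combined.
- For each procedure separately, report cumulative incidence with death as the competing event. Do not treat diversion as a competing event for transplantation. Section 3.1 admits patients after diversion and continues the calls after either procedure; a transplant that follows a diversion must still be counted.
- State that these estimates assume non-informative censoring and may still be low if patients who leave are at higher risk.

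The cost is SAP wording and some programming on event and last-contact dates, which the planned curves already need. No new data are required. The downside is that late event rates will be somewhat higher and their intervals wider.
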